3.8.2.2.1. Primary Analysis

The primary analyses will be carried out using a logistic regression model based on MI for missing data as described in Section 3.8.2.1.1. Proportion of subjects with ≥10% Weight Gain at Week 24 will be derived based on the same complete datasets obtained from the multiple imputation procedure. The logistic regression model will include the treatment group, race (Black or African American, Non-Black or African American), and age (<30, ≥30 years) as factors; and the baseline weight as the covariate. For subjects who prematurely discontinue the study drug but are willing to come back for weight assessments, only on-treatment weight assessments will be included in the primary analyses.

Similarly to the primary efficacy endpoint of percent change from baseline body weight at Week 24, the independent test statistic before and after the interim analysis will be combined using the CHW method with a fixed weight of $\sqrt{0.5}$ based on the original sample size. The treatment effects and 95% CIs will be reported as described in Section 3.8.2.1.1.

3.8.2.2.2. Sensitivity analysis

To assess the robustness of the primary analysis of the primary endpoint, the following sensitivity analyses will be performed:

- To assess the potential impact of missing data due to missing not at random (MNAR), the delta-adjusted Pattern Mixture Model in [Section 3.8.2.1.2](#) will be conducted to assess the impact of missing data. Proportion of subjects with $\geq 10\%$ Weight Gain at Week 24 will be derived based on the same complete datasets obtained from the multiple imputation procedure in [Section 3.8.2.1.2](#). The logistic regression model as in the primary analysis will be fitted to obtain the treatment effect estimate and standard error. Rubin's rule will be used to combine the treatment effect estimates and standard errors across imputations.
- To further assess the potential impact of missing data due to missing not at random (MNAR), the approach described in [Section 3.8.2.2.1](#) will be repeated including both on-treatment and off-treatment weight assessments after premature discontinuation of study drug.
- The logistic regression model may also adjust for additional covariates and/or factors, including but not limited to, study region or study sites.
- Average treatment difference across visits through Week 24 between ALKS 3831 and OLZ will be analyzed.

3.8.2.2.3. Additional Analyses

To assess the impact of different cutoffs for weight gain (ie, 5%, 7%, 10%, etc), a plot of cumulative responder distribution at Week 24 for each treatment group will be presented. The horizontal axis will present percent weight gain, and the vertical axis will present the proportion of subjects with weight gain. The analysis will be based on MI imputation for missing data.

3.8.3. Key Secondary Endpoint

The key secondary endpoint is the proportion of subjects with $\geq 7\%$ weight gain at Week 24. The primary analysis will be carried out using a logistic regression model based on MI without CHW adjustment as described in [Section 3.8.2.2.1](#). The sensitivity analysis will be the same as [Section 3.8.2.2.2](#).

3.8.4. Multiple Comparison/ Multiplicity

The study will be claimed positive when the primary analyses of both co-primary efficacy endpoints are statistically significant based on the CHW method to adjust for the unblinded interim analysis for sample size re-estimation; therefore, both co-primary endpoints will be tested at a full α level of 0.05. A fixed sequence approach will be used to control overall Type I error rate for the primary and key secondary endpoints. Only if both primary endpoints are statistically significant based on the CHW method will the key secondary endpoint be further tested at an alpha level of 0.05.

3.8.5. Examination of Subgroups

Subgroup analyses of the primary endpoints will be performed for each of the following categories:

- Sex (male, female)
- Age (<30 years, ≥30 years)
- Race (Black or African American, Non-Black or African American)
- BMI (<27 kg/m², ≥27 kg/m²)

The forest plot of the least squares mean difference along with 95% CIs in percent change in body weight from baseline at Week 24 between ALKS 3831 and OLZ will be provided by the subgroup factors listed above.

3.8.6. Other Efficacy Endpoints

- Percent change from baseline in body weight at Week 24 in the Early Weight Gain population
- Proportion of subjects with ≥10% weight gain at Week 24 in the Early Weight Gain population
- Change from baseline in fasting lipids (fasting triglycerides, LDL, HDL, total cholesterol), fasting glucose, fasting insulin and HbA1c by visit
- Absolute change in body weight by visit
- Change from baseline in waist circumference by visit
- Change from baseline in PANSS total score and subscales by visit
- Change from baseline in Clinical Global Impression-Severity (CGI-S) by visit
- CGI-I score by visit
- Change from baseline in Impact of Weight on Quality of Life (IWQOL)-Lite total score and subscales by visit
- Change from baseline in EuroQol five dimensions questionnaire (EQ-5D)-5L score by visit

The following endpoints will be analyzed similarly by ANCOVA model and MI for missing data as noted in [Section 3.8.2.1.1](#), without CHW adjustment:

- Percent change from baseline in body weight at Week 24 in the Early Weight Gain population
- Absolute change in body weight by visit
- Change from baseline in waist circumference by visit

Proportion of subjects with ≥10% weight gain at Week 24 in the Early Weight Gain population will be analyzed similarly by logistic regression model and MI for missing data as described in [Section 3.8.2.2.1](#), without CHW adjustment.

Change from baseline in fasting lipids (fasting triglycerides, LDL, HDL, total cholesterol), fasting glucose, fasting insulin and HbA1c will be analyzed by the same MMRM model as described in [Section 3.8.2.1.2](#). The model will include treatment, visit, treatment-by-visit interaction term, race (Black or African American, Non-Black or African American) and age (<30, ≥30 years) as categorical fixed effects; the baseline value will be included as the covariate.

MMRM model will also be applied to the following endpoints:

- Change from baseline in PANSS total score and subscales by visit
- Change from baseline in Clinical Global Impression-Severity (CGI-S) by visit
- Change from baseline in Impact of Weight on Quality of Life (IWQOL)-Lite total score and subscales by visit
- Change from baseline in EuroQol five dimensions questionnaire (EQ-5D)-5L score by visit

The model will include treatment, visit, treatment-by-visit interaction term as categorical fixed effects; the baseline value will be included as a covariate.

PANSS responder status (<20%, ≥20% improvement over baseline PANSS), CGI-I score, and CGI-I responder status (≤2 versus >2) at each visit will be summarized by descriptive statistics.

IWQOL-Lite scale is a 31-item self-report measure of obesity-specific quality of life. The IWQOL-Lite provides an overall total score as well as scores on five domains: (1) physical function, (2) self-esteem, (3) sexual life, (4) public distress, and (5) work. The raw IWQOL scores will be transformed as follows ([Tessier et al, 2012](#)) before analyzed by the MMRM method. The transformed scores range from 0 to 100, with 100 representing the best and 0 the most impaired quality of life.

$$\text{Transformed Score} = \frac{\text{maximum theoretical score} - \text{actual score}}{\text{test score range}} \times 100$$

The EQ-5D-5L is a validated quality of life questionnaire developed by the EuroQol Group in order to provide a simple, generic utility measure for characterizing current health states of patients. EQ-5D-5L is designed for self-completion by subjects. It consists of 2 parts – the EQ-5D-5L descriptive system and the visual analogue scale (VAS).

The EQ-5D-5L descriptive system comprises 5 dimensions: mobility, self-care, usual activities, pain/discomfort, and anxiety/depression. Each dimension has 5 levels.

The 5 dimensional 5-level systems are converted into an index value. Values for theoretically possible health states are calculated using a regression model and weighted according to the social preferences of the U.S. population ([Van Hout et al, 2012](#)). The VAS records the respondent's self-rated health on a vertical visual analogue scale. The VAS 'thermometer' has 100 (Best imaginable health state) at the top and 0 (Worst imaginable health state) at the bottom. This information can be used as a quantitative measure of health outcomes as judged by the individual respondents. EQ-5D-5L self-reported VAS data generates information on the self-perceived overall health-related quality of life.

Additional analyses of metabolic laboratory parameters, body weight, and PANSS total score are included in the [Exploratory Statistical Analysis Plan \(ESAP\)](#) conducted outside the scope of this SAP.

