**Table 3: Schedule of Visits and Assessments (Continued)**

Visit	Screening Day -30 to -1	24-Week Double-Blind Treatment																Safety Follow- up a		Monthly Visits b	
	1	2 c	3	4	5	6	7	8	9	10	11	12	13	14	15	16	17/ET	18	19	20 to 24	
Study Week (Visit Window of ±2 Days for Visits 3-24)			1	2	3	4	5	6	8	10	12	14	16	18	20	22	24	26	28		
Biochemistry, Urinalysis, and Hematology Samples n	X	X	X	X		X			X		X		X		X		X				
Vital Signs i	X	X	X	X		X		X	X		X		X		X		X		X		
Body Weight and Waist Circumference j	X	X	X	X		X		X	X		X		X		X		X	X	X	X j	
AE Monitoring	X	X	X	X	X	X	X	X	X	X	X	X	X	X	X	X	X	X	X	X	X k
Concomitant Medication Review l	X	X	X	X	X	X	X	X	X	X	X	X	X	X	X	X	X	X	X	X	X m
C-SSRS n	X	X	X	X	X	X	X	X	X	X	X	X	X	X	X	X	X	X	X	X	
Psychiatric Efficacy/ Lifestyle/ Quality of Life Assessments																					
PANSS o	X	X		X		X		X	X		X		X		X		X				
CGI-S	X	X		X		X		X	X		X		X		X		X				
CGI-I				X		X		X	X		X		X		X		X				
Cigarette Use Questionnaire		X				X		X	X		X		X		X		X				
IWQOL-Lite		X				X					X						X				
EQ-5D		X				X					X						X				

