## Other Endpoints

Other endpoints are:

- Percent change from baseline in body weight at Week 24 in the early weight gain population
- Proportion of subjects with  $\geq 10\%$  weight gain at Week 24 in the early weight gain population
- Change from baseline in fasting lipids (fasting triglycerides, low-density lipoprotein [LDL], high-density lipoprotein [HDL], total cholesterol), fasting glucose, fasting insulin, and HbA1c by visit
- Absolute change in body weight by visit
- Change from baseline in waist circumference by visit
- Change from baseline in PANSS total score and subscales by visit
- Change from baseline in CGI-S by visit
- CGI-I score by visit
- Change from baseline in IWQOL-Lite total score and subscales by visit
- Change from baseline in EQ-5D score by visit

The body weight- and waist circumference-related endpoints will be analyzed in the same manner as the co-primary endpoints. An ANCOVA model will be used for continuous endpoints. The model will include treatment group, race (Black or African American, non-Black or African American), and age ( $<30$ ,  $\geq 30$ ) as factors, and baseline value as a covariate. A logistic regression model will be used for categorical endpoint, adjusting for the same covariates. Missing values will be addressed by an MI approach.

Change from baseline in fasting lipids (fasting triglycerides, LDL, HDL, total cholesterol) and fasting glucose, fasting insulin, and HbA1c will be analyzed by a mixed model with repeated measurements (MMRM) model. The model will include treatment, visit, treatment-by-visit interaction term, race (Black or African American, non-Black or African American) and age ( $<30$ ,  $\geq 30$ ) as categorical fixed effects; the baseline value will be included as a covariate.

Change from baseline in PANSS, CGI-S, IWQOL-Lite and EQ-5D will be analyzed by MMRM model. The model will include treatment, visit, and treatment-by-visit interaction term as categorical fixed effects; the baseline value will be included as a covariate.

PANSS responder status ( $<20\%$ ,  $\geq 20\%$  improvement over baseline PANSS), CGI-I score, and CGI-I responder status ( $\leq 2$  vs  $>2$ ) will be presented by summary statistics.

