3.8. Efficacy Analyses

3.8.1. General Considerations

All statistical tests will be 2-sided hypothesis tests performed at the 5% significance level. All confidence intervals will be 2-sided 95% confidence intervals.

Baseline for the primary efficacy analysis is defined as the last non-missing observation on or before the first dose of study drug in the double-blind treatment period.

Only the on-treatment weight assessments will be included in the analyses, unless specified otherwise.

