- Average treatment difference across visits through Week 24 between ALKS 3831 and OLZ will be analyzed using mixed model with repeated measurements (MMRM) model. The MMRM model will include treatment, visit, treatment-by-visit interaction term, race (Black or African American, Non-Black or African American) and age (<30, ≥ 30 years) as categorical fixed effects; baseline weight will be included as a covariate. An unstructured covariance structure will be applied. The Kenward-Roger approximation ([Kenward and Roger 1997](#)) will be used to adjust the denominator degree of freedom. The analysis will be performed on all observed post-randomization on-treatment weight measurements without imputation of missing data.

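### The by-visit MMRMs in SAP 3.8.6 omit a baseline-by-visit term, which costs some Week 24 precision if the baseline slope changes over time

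*SAP*

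**What the plan says.** SAP 3.8.6 analyses two groups of endpoints by MMRM.

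- **Fasting lipids, glucose, insulin, HbA1c.** The section refers back to the MMRM of SAP 3.8.2.1.2, lists treatment, visit, treatment-by-visit, race and age group, and ends "the baseline value will be included as the covariate".
- **PANSS, CGI-S, IWQOL-Lite, EQ-5D-5L.** "The model will include treatment, visit, treatment-by-visit interaction term as categorical fixed effects; the baseline value will be included as a covariate".

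Protocol 14.4 (Other Endpoints) has the same form for the second group: "The model will include treatment, visit, and treatment-by-visit interaction term as categorical fixed effects; the baseline value will be included as a covariate". The body-weight MMRM in SAP 3.8.2.1.2 reads "baseline weight will be included as a covariate. An unstructured covariance structure will be applied". Neither document adds a baseline-by-visit term anywhere.

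The unstructured covariance is stated for the weight MMRM and reaches the laboratory endpoints by cross-reference. No covariance structure is stated for PANSS, CGI-S or the two questionnaires.

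Protocol Table 3 gives the post-baseline visits:

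- laboratory endpoints: Weeks 1, 2, 4, 8, 12, 16, 20, 24
- PANSS and CGI-S: Weeks 2, 4, 6, 8, 12, 16, 20, 24
- IWQOL-Lite and EQ-5D: Weeks 4, 12, 24

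**The concern.** In these models the mean and the treatment effect may change from visit to visit, and so may the covariance where it is unstructured. The baseline slope may not. A measurement two weeks after baseline usually tracks baseline more closely than one taken at 24 weeks, so the best adjustment can differ between visits. A shared slope is then a compromise. If it lies nearer the early-visit slopes, baseline variation is left in the Week 24 residual and the Week 24 interval is wider than it need be.

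The endpoints are defined by visit, so visit-specific contrasts are what would be reported. They bear on the metabolic effect and on whether antipsychotic effect is preserved. Dropout raises a second question: a wrong slope can bias the contrast if those who leave differ between arms.

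**Working it through.** **The plan's own figure.** The only power statement (SAP 2, Protocol 14.1) is at least 90% for the two primary endpoints at 200 per arm. It reproduces: 99.4% for 3% versus 7% with SD 9%, and 89.9% (pooled variance) or 90.4% (unpooled) for 14% versus 27%. No power is stated for the MMRM endpoints.

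**Formulas.** Let ρ_t be the correlation of the week-t value with baseline.

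- Slope of change on baseline at week t: b_t = ρ_t × (SD_t / SD_0) − 1.
- Shared slope: b_c = (1′S⁻¹b) / (1′S⁻¹1), where S is the residual covariance under that slope, iterated to convergence.
- Week 24 variance inflation with complete data: 1 + (b_24 − b_c)² × Var(baseline) / Var(Week 24 change given baseline).

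**Assumed inputs.** The documents give no correlations or SDs. The correlation at a given lag is taken as c + (1 − c − nugget) × 0.5^(lag/half-life), with c 0.3-0.6, nugget 0.1-0.3 and half-life 4-12 weeks. Across the laboratory and PANSS schedules this gives about 0.58-0.88 at the first visit. For the questionnaires, first measured at Week 4, the same formula gives 0.50 (0.3 + 0.4 × 0.5) to 0.84 (0.6 + 0.3 × 0.5^(4/12)). At Week 24 it gives 0.31-0.68. An unstructured covariance is assumed for all endpoints.

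**One case by hand** (laboratory schedule, c 0.45, nugget 0.2, half-life 8 weeks, baseline SD 1):

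- ρ at Week 24 = 0.45 + 0.35 × 0.5³ = 0.494; ρ at Week 1 = 0.45 + 0.35 × 0.5^(1/8) = 0.771.
- Equal SDs: b_1 = −0.229, b_24 = −0.506, b_c = −0.321. Inflation = 1 + 0.1856² / (1 − 0.494²) = 1 + 0.0344 / 0.756 = 1.046.
- SD rising linearly by 30% to Week 24: b_24 = 0.494 × 1.3 − 1 = −0.358, b_c = −0.258. Inflation = 1 + 0.1004² / (1.69 × 0.756) = 1.008.

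**Whole grid, Week 24 variance inflation:**

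| Endpoints | Equal SDs: range | Equal SDs: median | SD +30%: median |
|---|---|---|---|
| Laboratory | 0.2-15% | 4% | 0.8% |
| PANSS | 0.1-10% | 3% | 0.6% |
| Questionnaires | 0.1-6.5% | 1.5% | 0.4% |

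Interval width grows with the square root: √1.042 = 1.021 at the laboratory median and √1.149 = 1.072 at its maximum.

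**A second set of correlation patterns**, also with equal SDs. A correlation of 0.9 or 0.85 falling to 0.5 or 0.6 gives a Week 24 SE 1.6-6.5% larger. An extreme fall from 0.95 to 0.3 gives 13.7% for laboratory endpoints, 10.6% for PANSS and 6.8% for the questionnaires. Constant slopes give zero.

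**Dropout.** MMRMs were simulated at 200 per arm with no true effect, the correlation falling from 0.9 to 0.5, and 36-39% missing at Week 24 (all assumed). The PANSS and questionnaire schedules were used.

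- Same outcome-dependent mechanism in both arms: bias below 0.005 SD under either model; the planned model's SD is 4-5% larger.
- Outcome-dependent dropout in one arm only: the planned model has a bias of about 0.05-0.06 SD and type I error of 7.7-9.0%. With baseline-by-visit, bias is below 0.01 SD and type I error 5.1-5.4%.
- Flat slopes with one-arm dropout (questionnaire schedule): no material bias, and an SD ratio of 0.997, so the extra terms cost essentially nothing.

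**The case against.** The strongest reply is that the loss is conditional and may be negligible. A falling correlation does not by itself make the slope more negative, because the slope also depends on the SD ratio. With a correlation falling from 0.85 to 0.65 and an SD rising 30%, the slopes are −0.15 and 0.65 × 1.3 − 1 = −0.155, so nothing is lost. A rising SD is plausible here. Eligibility truncates baseline PANSS to 50-90 and CGI-S to 4 or less (Protocol 7.1) and caps HbA1c, glucose, cholesterol and triglycerides (7.2.5), while later values are not restricted in that way. This stands, and it is why the size must be given as conditional.

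A reader might also infer three stronger points that the documents do not support.

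- **That the HbA1c withdrawal rule biases the glycaemic comparisons.** The rule in Protocol 7.3 is the same in both arms, and it acts after subjects with HbA1c of 6.0% or more, or a history of diabetes, have been excluded. In simulation, a mechanism common to both arms gave no bias.
- **That these models carry all the model-based evidence on metabolic and antipsychotic effect.** SAP 3.8.6 places further analyses of metabolic parameters and PANSS in a separate exploratory plan, which is not available here.
- **That the weight MMRM in SAP 3.8.2.1.2 suffers the same Week 24 loss.** It targets the average difference across visits, so the Week 24 figures do not carry over.

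**Conclusion.** The omission is certain from the text; its cost is conditional. One baseline slope is imposed on all visits, starting at Week 1 only for the laboratory endpoints, at Week 2 for PANSS and CGI-S, and at Week 4 for the questionnaires. If the slope drifts, typical precision losses at Week 24 are a few percent of variance with equal SDs and under 1% if the SD grows by 30%. The figures rest on assumed correlations, complete data and an unstructured covariance, which the SAP does not state for PANSS, CGI-S or the questionnaires.

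Bias needs two conditions together, drifting slopes and outcome-dependent dropout that differs by arm. The documents establish neither.

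The affected endpoints are classed as other endpoints, outside the fixed sequence of SAP 3.8.4. The primary and key secondary analyses use multiple imputation with ANCOVA or logistic regression at Week 24 and do not change. This is a minor improvement available at almost no cost. It does not threaten the trial's main conclusions.

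**What to change.** In SAP 3.8.6, specify for both MMRM groups: *fixed effects treatment, visit, treatment-by-visit, baseline value and baseline-by-visit interaction*. Keep race and age group where they are already listed. Align Protocol 14.4, or record the change in SAP section 5.

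For consistency the same term may be added to the weight MMRM in SAP 3.8.2.1.2; no Week 24 gain is claimed there.

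The cost is one slope per visit instead of one in all: 8 − 1 = 7 extra parameters for the eight-visit endpoints and 3 − 1 = 2 for IWQOL-Lite and EQ-5D-5L, against a planned 400 subjects. Data collection and trial conduct do not change.

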3.8.7. Exploratory Endpoints

Body composition is assessed in the substudy at Visit 2 (Week 1) and Visit 17/ET (Week 24) for a subset of subjects by the following exploratory endpoints:

- Absolute change from baseline in lean mass
- Absolute change from baseline in fat mass
- Change from baseline in percent body fat

These endpoints will be analyzed by the ANCOVA method adjusting for race (Black or African American, Non-Black or African American), and baseline age (<30, ≥30 years) as factors and corresponding baseline value as covariate for the subset of subjects with baseline and post-baseline body composition assessments.

3.9. Safety Analysis

3.9.1. Adverse Events

Adverse events will be coded by System Organ Class and Preferred Term using the Medical Dictionary for Regulatory Activities (MedDRA[®]) Version 21.0. The verbatim term will be included in the AE listings.

An AE (classified by preferred term) will be considered as treatment-emergent AE (TEAE) if the event is newly occurring or worsening on or after the date of first dose of study drug.

The number and percentage of subjects reporting TEAEs during the double-blind treatment period in each treatment group will be presented by treatment group for the following categories:

- System organ class and preferred term
- Preferred terms in decreasing frequency, and also including the following subsets:
 - Experienced by ≥2% of subjects in any treatment group
 - Experienced by ≥5% of subjects in any treatment group and ≥2 times of OLZ group
- System organ class, preferred term, and severity
- System organ class, preferred term for severe TEAEs
- System organ class, preferred term, and relationship
- System organ class, preferred term for drug-related TEAEs

The number and percentage of subjects reporting TEAEs during the double-blind treatment period between Visit 6 (Week 4) to Visit 17 (Week 24) will be presented by treatment group, OLZ dose levels at Visit 6 and preferred terms.

If more than one AE is coded to the same preferred term for the same subject for the same period, the subject will be counted only once for that preferred term using the most severe and most related occurrence for the summarization by severity and by relationship to study drug.

In addition, the number and percentage of subjects reporting AEs during the Safety Follow-up Period will be tabulated by the system organ class, preferred term and treatment group.

For the subjects who prematurely discontinue the study drug and return for the monthly visits, all AEs collected after discontinuation of the study drug will be summarized by system organ class, preferred term and treatment group.

The number and percentage of subjects who have serious adverse events (SAE) and AEs leading to premature discontinuation from the treatment will be summarized by preferred term and treatment group and will be sorted by decreasing frequency for ALKS 3831 group.

